 - Key identified risks associated with AT132 administration observed in Study ATX-MTM-002 are listed below. Of the overall risks associated with rAAV gene therapy, thrombotic microangiopathy and sensory ganglionopathy have not been observed in ATX-MTM-002 study subjects. Long-term follow-up is important in understanding whether these AEs have long-term implications. Refer to the Investigator's Brochure for further details.
 - **Hepatobiliary events:** Many XLMTM patients have liver dysfunction and cholestasis, which places them at increased risk for hepatobiliary dysfunction or even hepatic failure with rAAV administration. A prospective natural history study (Study ATX-MTM-009) reported that overall, 91% of subjects had histories of hepatic

disease and/or prospectively experienced related AEs or laboratory or imaging abnormalities (Dowling, 2022).

- In Study ATX-MTM-002, SAEs due to hepatobiliary dysfunction occurred after AT132 administration and were characterized by hyperbilirubinemia, cholestatic liver dysfunction, transaminases elevations, ascites, and serum bile acid elevations. Fatal outcomes were observed in 4 subjects due to multifactorial causes including hepatobiliary failure: 1 subject who received the 1.0×10^{14} vg/kg dose and 3 subjects who received the 3.0×10^{14} vg/kg dose. All 4 subjects showed increases in direct and total bilirubin values (> upper limit of normal [ULN]) beginning 1 to 4 weeks after AT132 administration (Shieh, 2023). Liver findings included intrahepatocellular and canalicular cholestasis, periportal and bile ductular reaction, secondary fibrosis, and notable lack of prominent liver parenchymal inflammatory cellular infiltrates (Shieh, 2020).
- **Myocardial events:**
 - *Acute cardiac risks:* Acute myocardial events manifested as myocarditis and increases in troponins. In Study ATX-MTM-002, variable increases in troponin levels after AT132 administration were commonly observed. Two subjects experienced SAEs of myocarditis: 1 subject who received the 1.0×10^{14} vg/kg dose and 1 subject who received the 3.0×10^{14} vg/kg dose. Prolonged prednisolone administration plus addition of other immunosuppressive medications were used for treatment of myocarditis.

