3.0	10-Jan-2024	Baseline Definition (4.10.1)	Baseline definition updated to exclude information from INCEPTUS study.	Aligning SAP to protocol Amendment version 11.0
3.0	10-Jan-2024	Analysis Windows	Analysis windows have been updated to accommodate the longer follow-up to align to Protocol V 11.0. Additional details on windowing daily diary data have been added	Aligning SAP to protocol Amendment version 11.0; adding details for clarity of definitions
4.0	15-Apr-2024	Protocol Deviations (4.2.2)	Category definition for the protocol deviations has been updated.	Aligning SAP to Protocol Deviation Plan
4.0	15-Apr-2024	Percentage of participants achieving full ventilator independence at Week 24 (4.4.2.2.7)	The following statement has been removed: "Note: this endpoint definition is different from what is specified in the protocol at the time of SAP development (V11.0). It was updated from "Percentage of participants achieving full ventilator independence in the absence of acute illness and perioperatively at Week 24" to "Percentage of participants achieving full ventilator independence at Week 24" in the SAP".	Aligning SAP to protocol Amendment version 12.0

SAP Version	Approval Date	SAP Section(s)	Change	Rationale
4.0	15-Apr-2024	Table 6. Potentially Clinically Significant Criteria for Vital Signs (4.6.2.3) Table 7. Potentially Clinically Significant Criteria for ECG (4.6.2.4)	For Age Group, "> 7 years" has updated to "≥ 8 years".	For clarification purpose.
4.0	15-Apr-2024	Hospitalization (4.6.2.5.3)	Category definition for the annualized hospitalization rate has been updated.	Correcting a typographical error
4.0	15-Apr-2024	Analysis Windows (4.10.2)	Analysis windows have been updated according to schedule of assessment in Protocol V 11.0. Additional details have been added for analysis week windows for weekly average hours of ventilator support from diary of ventilator dependence.	Aligning SAP to schedule of assessments in protocol; analysis visit windows should have varied across endpoints based on protocol-defined visit schedule
4.0	15-Apr-2024	Appendix 2 Unfavorable Values for Efficacy Estimand Imputation (5.2)	An item of "Reduction in require ventilator support to ≤ 16 hours/day" has been removed.	Not needed to apply the imputation rule for this variable

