1.1.3 Estimand

The estimand of the primary objective is defined by the following 5 attributes:

- Treatment: Single dose of AT132
- Population: Male participants with ventilator-dependent XLMTM, as defined by the inclusion/exclusion criteria of the study
- Endpoint: Change from baseline in hours per day of ventilation support at Week 24
- Intercurrent events and their corresponding strategies: For study discontinuation due to death or due to lack of efficacy, a composite strategy will be adopted, where participants with the intercurrent event before Week 24 having missing observation(s) after the intercurrent event will have those missing observations(s) imputed by unfavorable values ([Appendix 2](#))
- Population level summary: Mean change from baseline, by AT132 dose level

The estimand framework described above will be applied to all relevant primary and secondary efficacy endpoints.

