4.4.2.2 Main Analytical Approach

The secondary efficacy analyses will be conducted for the FAS.

4.4.2.2.1 Time to reduction in required ventilator support to ≤ 16 hours a day (only in participants who require invasive ventilation) at Week 24

This endpoint will be summarized for low dose and the high dose groups separately in the participants who require invasive ventilation. Kaplan-Meier plots along with median (95% CI) time from the study start date to event will be provided.

The number of hours of ventilator support at each collected time point for this analysis will be taken directly from the daily diary (Protocol V5.0 and later) or by assessment of time off ventilator questionnaire (prior to Protocol V5.0). The first instance of time reduction reported as ≤ 16 hours per day will be considered an event. Participants will be censored at either Week 24 or withdrawal from study, whichever occurs first.

4.4.2.2.2 Change from baseline in Children's Hospital of Philadelphia Infant Test of Neuromuscular Disorders (CHOP INTEND) at Week 24

The change from baseline will be analyzed using the MMRM in a similar method to that used for the primary analysis of the primary efficacy endpoint, described in [Section 4.3.2](#).

Estimated change from baseline in CHOP INTEND score at Week 24 will be summarized by dose level.

In addition, the CHOP INTEND score and corresponding change from baseline at each visit will be summarized descriptively by dose level group.

The CHOP INTEND is an assessment scale that was originally designed to quantify motor abilities in infants aged 1.4 to 37.9 months, with spinal muscular atrophy type I (SMA-I) ([Glanzman, 2010](#)) and has been validated for XLMTM ([Duong, 2021](#)). The scale contains 16 questions, each of which is scored on a scale of 0 to 4, with 0 being no response/ability to perform the movement and 4 highest ability to perform the task, per CHOP INTEND item instructions.

The score used for analysis is the total sum of all 16 questions, which will range from 0 to 64. Higher score indicates better neuromuscular function. If an item is missing or scored as "Could Not Test (CNT)" then 0 will be imputed for the item score.

If a participant has 2 assessments with a total score of ≥ 56 , the CHOP INTEND will not be required for future visits.

Subject line plots of the CHOP INTEND over time will be created.

4.4.2.2.3 Change from baseline in maximal inspiratory pressure (MIP) at Week 24

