4.5.1.2 Main Analytical Approach

4.5.1.2.1 Time to unassisted sitting for 30 seconds or more at Week 24

This endpoint will be summarized for low dose and the high dose groups separately for all participants in the FAS. Kaplan-Meier plots along with median (95% CI) time from the study start date to event will be provided.

The event of successful unassisted sitting for 30 seconds is defined as described in [Section 4.4.1.1](#). Participants who meet the described criteria will be considered to have an event. All other participants will be censored

4.5.1.2.2 Change from baseline in the Motor Function Measure-32 (MFM-32) at Week 24

MFM-20 and MFM-32 total and dimension scores will be summarized descriptively by visit and dose level group. For the MFM-20 by-visit summary, if participants were administered the MFM-32, then the MFM-20 questions/derivations will be used from those assessments to derive the MFM-20 result for summary purposes.

Regardless of whether the participants were administered MFM-32 or MFM-20, the observed total and dimension scores and corresponding change from baseline at each visit will be listed. The listing will include a column indicating which version of the questionnaire was administered at the visit.

4.5.1.2.2.1 MFM-32 Scoring

The MFM-32 contains 32 items to assess motor function, each measured on a scale of 0 to 3, for a total score of 96. The measures capture 3 dimensions of motor function:

- Standing and transfers (D1: 13 Items 6, 8, 11, 12, 24, 25, 26, 27, 28, 29, 30, 31 and 32)
- Axial and proximal motor function (D2: 12 Items 1, 2, 3, 5, 7, 9, 10, 13, 14, 15, 16 and 23)
- Distal motor function (D3: 7 Items 4, 17, 18, 19, 20, 21, and 22)

The score for each dimension corresponds to the sum of the scores obtained by the person for the items of this dimension divided by the maximum score for this dimension and multiplied by 100. For the unilateral items, the best score of the two sides at each visit will be used.

For the MFM-32, the total score is the sum of the 32 items scores divided by 96, as shown in the table below:

Table 2 MFM-32 Scoring

Measurement	Calculation
D1: Standing and Transfers	$D1\% = \frac{\text{Sum of D1 score}}{13 \times 3 = 39} * 100$
D2: Axial and Proximal	$D2\% = \frac{\text{Sum of D2 score}}{12 \times 3 = 36} * 100$
D3: Distal Motor Function	$D3\% = \frac{\text{Sum of D3 score}}{7 \times 3 = 21} * 100$
Total	$\text{Total}\% = \frac{\text{Sum of total score}}{32 \times 3 = 96} * 100$

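### The SAP does not say how death is handled in the time to at most 16 h/day of ventilation; on its natural reading, event-free deaths and lack-of-efficacy discontinuations are censored when they occur, which is inconsistent with its composite strategy and can only raise the response estimate

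*SAP*

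**What the plan says.** SAP 4.4.2.2.1 restricts this secondary endpoint to invasively ventilated children and takes the hours straight from the diary or the questionnaire. It plans Kaplan-Meier curves with a median and 95% CI for each dose. Its event and censoring rule is that a first report of at most "16 hours per day will be considered an event. Participants will be censored at either Week 24 or withdrawal from study, whichever occurs first". The section does not mention death, lack of efficacy or a competing-risk method.

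Other parts of the SAP bear on how that rule is read:

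- SAP 1.1.3 treats death and lack of efficacy as reasons for study discontinuation and handles both with a composite strategy: missing values afterwards become unfavourable values. On scope it says "The estimand framework described above will be applied to all relevant primary and secondary efficacy endpoints".
- SAP 4.3.2 sets the hours of ventilation to 24 after such an event. Appendix 2 repeats this and sets full ventilator independence to No.
- Appendix 2 has no row for the 16 h/day endpoint. The version history shows that v4.0 removed it, with the reason "Not needed to apply the imputation rule for this variable".
- SAP 4.4.2.2.8 (Survival) refers to death as one of the reasons for which a child may withdraw.
- SAP 4.5.1.2.1, the exploratory time to unassisted sitting, says "Participants who meet the described criteria will be considered to have an event. All other participants will be censored". It gives no censoring date and no rule for death.

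Deaths did occur. Protocol 1.5 states "Fatal outcomes were observed in 4 subjects due to multifactorial causes including hepatobiliary failure", one at the lower dose and three at the higher. It does not say how long after dosing they died.

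**The concern.** If death counts as withdrawal, a child who dies before reaching 16 h/day is censored on the day of death. Kaplan-Meier then assumes that his chance of later response equals that of the children still under observation, when it is zero. Discontinuation for lack of efficacy is censored in the same way, although the reason for leaving is itself information about response.

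The same child would be a failure on the primary endpoint and on ventilator independence, yet here he would simply leave the risk set. The curve and its median would describe weaning as if nobody died, while the two neighbouring ventilation endpoints count death against treatment. A reader comparing the three would not be comparing like with like.

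**Working it through.** The documents give no response figure for this endpoint, so there is no planned value to reproduce.

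**Step 1: which reading applies.** SAP 4.4.2.2.1 offers two censoring dates, Week 24 and withdrawal. SAP 1.1.3 speaks of discontinuing the study because of death, and SAP 4.4.2.2.8 counts death among the reasons for withdrawing. Together they place an event-free death at the withdrawal date. This is an inference, because 4.4.2.2.1 itself is silent.

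**Step 2: direction.** The estimated response probability at Week 24 is 1 − Π(1 − eᵢ/rᵢ), with eᵢ responses and rᵢ children at risk at each response time. Removing a child at death lowers every later rᵢ and so raises the estimate. Earlier terms do not change. The effect is therefore upward or nil. It is nil if the deaths follow the group's last response or fall after Week 24.

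**Step 3: size.** With n children, k responders and m event-free deaths:

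- deaths kept at risk to Week 24, no other early censoring: k/n
- deaths censored before any response: k/(n − m), so the ratio is n/(n − m)

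Inputs:

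- High dose: n = 17 (Protocol 1.4.2, cutoff 08 July 2020) and m up to 3 (Protocol 1.5). That all 17 were invasively ventilated is an assumption.
- Low dose: 5 of the first 6 were invasively ventilated (Protocol 1.4.2). One more child is inferred: 3 undosed controls (Protocol 3.1) less the 2 never dosed (SAP 1.3). Part 2 required invasive support, so n is about 6, assuming no replacement was enrolled. m is up to 1.
- Responder counts and all times are assumptions. Responses are spaced evenly over Weeks 6 to 23. Deaths come before all responses, or mid-course (about Weeks 10, 14 and 18 for the high dose; Week 14 for the low dose).

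| Group | Responders | Censored, deaths first | Censored, deaths mid-course | Deaths kept as non-responders |
|---|---|---|---|---|
| High, n = 17, m = 3 | 8 | 8/14 = 57.1% | 54.2% | 8/17 = 47.1% |
| High | 10 | 10/14 = 71.4% | 68.1% | 10/17 = 58.8% |
| High | 14 | 14/14 = 100% | 100% | 14/17 = 82.4% |
| Low, n = 6, m = 1 | 4 | 4/5 = 80.0% | 77.8% | 4/6 = 66.7% |
| Low | 5 | 5/5 = 100% | 100% | 5/6 = 83.3% |

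One mid-course value in full: with 8 high-dose responders, 1 − (15/17)(12/14)(10/11)(6/9) = 54.2%.

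With 8 high-dose responders the median is reached when deaths are censored (Week 20.6 with deaths first, Week 23.0 mid-course) and is not reached when they are kept. With 10 responders it moves from Week 21.1 to 17.3 or 19.2. The Aalen-Johansen cumulative incidence, with death as a competing event, gave the same Week 24 value as the last column in every scenario.

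**Step 4: dose comparison.** The largest inflation ratios are 17/14 = 1.21 for the high dose and 6/5 = 1.20 for the low dose.

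**The case against.** - **Death may not be a withdrawal.** Protocol 3.5.1 lists reasons for early withdrawal, and neither death nor lack of efficacy is among them. On that reading the child stays at risk to Week 24, which is the remedy proposed here. This stands as an ambiguity. SAP 1.1.3 and 4.4.2.2.8 point the other way, and the text should not leave it to the programmer.
- **The removal was deliberate.** The scope sentence is limited to relevant endpoints, and v4.0 took this variable out with a recorded reason. A reader might infer a flat contradiction, but a documented exclusion does not support that word. It is an inconsistency whose stated reason does not deal with death.
- **The Appendix 2 row may have been redundant**, since hours are still set to 24. That would work if imputed hours fed this analysis and follow-up ran to Week 24. But 4.4.2.2.1 takes the hours straight from the diary or questionnaire and stops at withdrawal.
- **The analysis is descriptive and survival is reported separately.** Both are true (SAP 2 and 4.4.2.2.8). No error rate or power is affected. But the curve and median are themselves the reported result, and a separate survival curve does not correct them.
- **Time to sitting.** A reader might see the same breach there. That endpoint is exploratory, and SAP 1.1.3 covers only primary and secondary endpoints. What remains is a missing censoring date and a missing rule for death.

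**Conclusion.** The point holds as an inconsistency in how death and lack-of-efficacy discontinuation are handled, resting on the natural but inferred reading of withdrawal. Under that reading the response estimate can only be too high. In the illustrations the excess runs from 0 to 17.6 percentage points for the high dose (100 − 82.4) and from 0 to 16.7 for the low dose (100 − 83.3). These figures rest on assumed responder counts and times, on all 17 high-dose children being eligible, and on an inferred low-dose number.

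Two stronger conclusions are tempting and unsupported. The first is that response is in fact overstated: this needs a child to leave event-free before Week 24 and another in his dose group to respond later, and the documents do not date the deaths. The second is that the rule favours the high dose because it had more deaths: the worst-case ratios are practically equal, and the number of invasively ventilated high-dose children is not given.

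**What to change.** In SAP 4.4.2.2.1, state that a child who dies or discontinues for lack of efficacy without the event stays in the risk set as a non-responder and is censored at Day 168. Alternatively, report cumulative incidence with death as a competing event, and still say how lack-of-efficacy discontinuation is treated. Censor other withdrawals at the last ventilation assessment. Align SAP 1.1.3 and Appendix 2, either by naming this endpoint as covered or by pointing to the rule in 4.4.2.2.1.

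For consistency, give the exploratory time to sitting (4.5.1.2.1) the same rule and a censoring date.

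The cost is about one sentence per section and a changed censoring date in the programming; no new data are needed. The response figure may come out slightly less favourable.

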Following the occurrence of fatal serious AEs (SAEs) in Study ATX-MTM-002, the Sponsor, in consultation with the DMC and external experts, evaluated the data and reassessed the benefit/risk profiles of the 1.0×10^{14} vg/kg and 3.0×10^{14} vg/kg dose levels. As of the data cutoff date of 08 July 2020, 5 subjects who received 3.0×10^{14} vg/kg AT132 developed AT132-related SAEs involving the hepatobiliary system. In 2 subjects, these SAEs resolved; in 3 subjects, fatal events occurred subsequent to severe cholestatic liver dysfunction. Within the 3.0×10^{14} vg/kg dose level cohort, 8 of 17 subjects (47.1%) experienced 26 SAEs considered related to AT132. In contrast, within the 6 subjects dosed at the 1.0×10^{14} vg/kg dose level, all of whom are ≥ 2 years from AT132 administration, 1 (16.7%) subject experienced 4 AT132-related SAEs, all resolved, and none involved the hepatobiliary system. In addition to a favorable safety profile observed in the subjects treated with 1.0×10^{14} vg/kg, a clinically meaningful benefit continues to be observed in this group at last follow-up. In this group, which had a mean 20.5 hours (SE 2.02) of ventilation per day at baseline ($n = 5$ [83.3%] with invasive ventilation; $n = 1$ [16.7%] with non-invasive ventilation), 5 out of 6 (83.3%) subjects were ventilatory independent at last follow-up (as of data cutoff date 08 July 2020). With respect to gross motor development, at baseline 5 of the 6 subjects did not perform any of the following major motor milestones: sit unassisted for 30 seconds, raise self to standing position, stand alone, or walk alone. At baseline, 1 subject did sit unassisted for 30 seconds but did not perform the remaining motor tasks. At last follow-up following AT132 administration at 1.0×10^{14} vg/kg, 5 out of 6 subjects performed all of these motor tasks, including walking alone. Regarding performance on the Children's Hospital of Philadelphia Infant Test of Neuromuscular Disorders (CHOP INTEND), this 1.0×10^{14} vg/kg group demonstrated a baseline mean score of 37.7 (SE 2.42). At last follow-up, performance had improved to a mean score of 56.5 (3.97).

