Each item of the questionnaire is measured on a 5-point likert scale from – 0 (Never) to 4 (Almost always). The module is composed of 25 items comprising 3 dimensions:

- About My Neuromuscular Disease (17 items)
- Communication (3 items)
- About Our Family Resources (5 items)
- Total Scale Score

Higher scales/scores indicate lower problems.

Scores are derived in the following way:

- Step 1: Transform Score

- Items are reversed scored and linearly transformed to a 0-100 scale as follows: 0=100, 1=75, 2=50, 3=25, 4=0.
- Step 2: Calculate Scores by Dimensions x
 - If more than 50% of the items in the scale are missing, the scale scores should not be computed, $x \text{ Mean score} = \frac{\text{Sum of the items}}{\text{number of items answered}}$.
 - If more than 50% of the items in the scale are missing, the Scale Scores should not be computed.
 - If 50% or more items are completed: Impute the mean of the completed items in a scale.
- Total Score: Sum of all the items over the number of items answered on all the Scales.

Per protocol, the parent-report version of the questionnaire is supposed to be administered. In the case that the child-report version of the questionnaire is administered, the scoring algorithm will be adjusted accordingly.

Total scores and corresponding change from baseline will each be analyzed by MMRM at Week 24 as described above and summarized descriptively by dose level group and visit.

4.4.2.2.6 Number (%) of age-appropriate clinically relevant gross motor function milestones attained through Week 24

Protocol versions 1 to 4:

Bayley and motor milestone collection was intermittent and not required in versions 1 – 4 of the protocol, so data may be missing for some participants at some visits. In addition, the motor milestone eCRF was not added until version 5.0 of the protocol. As such, the Bayley III item (referenced in [Table 1](#)) corresponding to each motor milestone will be used for the analysis of the motor milestone data collected under protocol version 1 – 4. If the Bayley III result is not available for the visit, but the participant attended the visit, then their result will be included in the summary as “missing”.

Protocol versions 5+:

The motor developmental milestones listed in [Table 1](#) below will be derived in form of Yes (achieved) and No (not achieved).

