When all items are missing, the total score will be missing. When there are some missing item scores (but other items are available), the score for the missing item(s) will be imputed as 0.

4.5.1.2.2.2 MFM-20 Scoring

The MFM-20 was developed after the original MFM-32, and is a subset of the MFM-32 questionnaire. Items from the MFM-32 that are not considered validated for the <6 years old population are skipped for the administration of the MFM-20, though the numbering of the items remains the same.

The MFM-20 contains 20 items assessing motor function, each measured on a scale of 0 to 3, for a total score of 60. The measures capture 3 dimensions of motor function:

- Standing and transfers (D1: 8 Items 6, 11, 12, 24, 25, 27, 30, 32)

- Axial and proximal motor function (D2: 8 Items 1, 3, 5, 7, 9, 10, 14, 23)
- Distal motor function (D3: 4 Items 4, 18, 21, 22)

The score for each dimension corresponds to the sum of the scores obtained by the person for the items of this dimension divided by the maximum score for this dimension and multiplied by 100. For the unilateral items, the best score of the two sides at each visit will be used. For the MFM-20, the total score is the sum of the 20 items scores divided by 60, as shown in the table below:

Table 3 MFM-20 Scoring

Measurement	Calculation
D1: Standing and Transfers	$D1\% = \frac{\text{Sum of D1 score}}{8 \times 3 = 24} * 100$
D2: Axial and Proximal	$D2\% = \frac{\text{Sum of D2 score}}{8 \times 3 = 24} * 100$
D3: Distal Motor Function	$D3\% = \frac{\text{Sum of D3 score}}{4 \times 3 = 12} * 100$
Total	$\text{Total}\% = \frac{\text{Sum of total score}}{20 \times 3 = 60} * 100$

The same missing data conventions described in [Section 4.5.1.2.2.1](#) will be used for the MFM-20 scoring.

4.5.1.2.3 Change from baseline in total raw score in the gross motor domain of the Bayley Scales of Infant and Toddler Development III (Bayley-III) at Week 24

The raw Bayley-III gross motor domain scores and corresponding change from baseline at each visit will be summarized descriptively by dose level group.

The motor domain of the Bayley III is a standard series of measurements to assess the motor (fine and gross motor subscales) development of infants and toddlers.

To calculate the raw scores the following steps will be required:

1. For each task performed the child can receive either a credit point (1) or no credit (0)
2. Establish the Basal aka “floor”:

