4.10 Additional Conventions

4.10.1 Baseline Definition

Unless otherwise specified, baseline is defined as the last assessment collected in ASPIRO study prior to time/date of dosing with study drug.

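### CHOP INTEND items that were simply not done are scored as no ability at every visit, baseline included, so incomplete testing is mixed with weakness; missing MFM items are treated the same way

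*SAP*

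**What the plan says.** SAP section 4.4.2.2.2 describes each CHOP INTEND item as scored 0 to 4, "with 0 being no response/ability to perform the movement". It continues: "The score used for analysis is the total sum of all 16 questions, which will range from 0 to 64". If an item is missing or was recorded as Could Not Test, "then 0 will be imputed for the item score". No visit is exempted and no minimum number of scored items is required.

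The total goes into an MMRM on change from baseline, modelled on the primary analysis. In addition, "the CHOP INTEND score and corresponding change from baseline at each visit will be summarized descriptively by dose level group". Under SAP section 4.10.1, unless otherwise specified, "baseline is defined as the last assessment collected in ASPIRO study prior to time/date of dosing with study drug". That definition does not require a complete assessment.

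For the MFM-32 (SAP section 4.5.1.2.2.1), when some items are available, "the score for the missing item(s) will be imputed as 0". The MFM-20 follows the same convention. A fully missing MFM gives a missing total.

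The SAP handles other incomplete results differently:
- **PedsQL:** no scale score if more than half the items are missing; otherwise the instruction is "Impute the mean of the completed items in a scale".
- **ACEND:** subdomain scores are means of the answered items, with no imputation.
- **Motor milestones:** a result absent at an attended visit is reported as missing, not as not achieved (sections 4.4.1.1 and 4.4.2.2.6).

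**The concern.** An item left blank says nothing about whether the child could do it. Scoring it 0 records it as complete inability. The estimand (SAP section 1.1.3 and Appendix 2) keeps unfavorable values for missing data after discontinuation for death or lack of efficacy. The item rule gives the same worst value to ordinary gaps, including gaps before dosing.

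Placement matters. After dosing, a zero works against the treatment. At baseline it lowers the starting point, and that child then shows a gain as soon as the item is tested and scored. Because change is measured from one baseline, one under-scored baseline carries into all of that child's later change values.

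The study now tests no hypothesis, so its efficacy output is the by-dose means and their intervals. In a low-dose group as small as the six children described in Protocol section 1.4.2, a few blank items in one child can move the group mean. The only planned sensitivity analysis (SAP section 4.3.3) concerns ventilation hours and would not show this.

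**Working it through.** **The SAP's own ranges.** CHOP INTEND 16 × 4 = 64; MFM-32 32 × 3 = 96; MFM-20 20 × 3 = 60. All three agree with the SAP.

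**Inputs.** Protocol section 1.4.2 reports that the six low-dose children "demonstrated a baseline mean score of 37.7 (SE 2.42") and reached a mean of 56.5 at last follow-up. The number of items untested at baseline, m, is not in the documents and is assumed below.

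**Scale.**
- Average ability per item: 37.7 / 16 = 2.36 points (possible range 0 to 4).
- Change to last follow-up: 56.5 − 37.7 = 18.8 points. Those children were all at least 2 years from dosing, so this is not the Week 24 change. It serves only as a yardstick.

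**False gain for one child.** Suppose there is no true change, and m items are blank at baseline and tested later. False gain = m × (true item score).

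| m | At average ability (2.36) | Share of 18.8 | Upper bound (4 per item) |
|---|---|---|---|
| 1 | 2.36 | 12.5% | 4 |
| 2 | 4.71 | 25.1% | 8 |
| 3 | 7.07 | 37.6% | 12 |

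The lower bound is 0, when the child truly could not do the item.

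**Effect on a raw group mean of six, one child affected.**
- m = 1: 2.36 / 6 = 0.39, at most 4 / 6 = 0.67.
- m = 2: 4.71 / 6 = 0.79, at most 8 / 6 = 1.33.
- m = 3: 7.07 / 6 = 1.18, at most 12 / 6 = 2.0.

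These are shifts in the raw mean. The baseline-adjusted MMRM estimate would move by a different amount, depending on the fitted baseline slope.

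**Other patterns.** An item tested at baseline but blank at Week 24 lowers the change by its true Week 24 score, again 0 to 4 points. An item blank at both visits contributes no change, whatever the child's true course.

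**Mean of scored items instead.** With m = 2 the zero-filled baseline is 37.7 − 4.71 = 32.99. Prorated, it is 32.99 × 16 / 14 = 37.7, so the false gain is 0. This holds only if the untested items are on average as hard for the child as the tested ones.

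**MFM.** One zero-filled item lowers the MFM-32 total by up to 3 / 96 = 3.1 percentage points and the MFM-20 total by up to 3 / 60 = 5.0. In the distal dimension the limits are 3 / 21 = 14.3 and 3 / 12 = 25.0.

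**The case against.** The best defence is that Could Not Test is a recorded outcome, and the instrument's instructions may assign it 0. The SAP version history says scoring algorithms were updated to match scoring instructions. Those instructions are not in the documents, so a reader who infers that 0 for Could Not Test is an error goes further than the text allows. This part of the objection stands. It does not cover an item that is merely missing, which the SAP lists separately and for which it cites no instruction.

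A second defence is that these are performance tests. A weak infant may leave an item undone because he cannot do it, and prorating would then credit ability never shown. This also stands in part. It makes zero-fill a reasonable sensitivity analysis and proration a debatable main rule, but it does not make every blank an inability.

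Third, gaps may be rare. The protocol lets assessments run over several days, excludes children with active infection, and has testing video recorded. No counts are given either way.

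Two further inferences are tempting and not supported. One is that a CHOP INTEND assessment skipped after two high totals would score 0. The rule speaks of an item, and Appendix 2 imputes a total of 0 separately after an intercurrent event, so the natural reading is that no assessment gives no score. The other is that MFM-32 totals would be capped at visits where only the MFM-20 was given. The SAP derives the MFM-20 from the MFM-32, not the reverse, and the listing shows which version was used.

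**Conclusion.** The concern holds for items that were simply not done. As written, the SAP scores them as inability, before and after dosing, with no minimum completeness. Each such item distorts one child's CHOP INTEND change by 0 to 4 points, about 2.4 at average low-dose ability. It inflates the change if the gap is at baseline and the item is later scored above 0, and deflates it if the gap comes after dosing.

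A reader might infer that the rule inflates the apparent drug effect. The documents do not support that: the number and timing of affected items are unknown, so the net direction is too. The 2.4 figure assumes that untested items are of average ability.

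No test or error rate is affected. CHOP INTEND is a supportive secondary endpoint, MFM is exploratory, and all summaries are descriptive. The point still deserves correction because the by-dose estimates are what will be reported, nothing planned would reveal the effect, and the remedy is cheap.

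**What to change.** 1. Separate not done from Could Not Test. Keep 0 for Could Not Test where the instrument's scoring instructions prescribe it, and cite them. Do not score not-done items as 0: set the total to missing when fewer than a stated number of items are scored, and otherwise use 16 times the mean of the scored items, in line with PedsQL.
2. State that the item rule applies only to assessments actually performed.
3. Report counts of missing and Could Not Test items by visit and dose. Show the Week 24 change under both zero-fill and the alternative scoring as a sensitivity analysis.
4. Apply the same rule to missing MFM items.

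The cost is a few sentences in the SAP, a small programming change and one extra table. The downside is that proration may overstate ability where an item was left undone because of true weakness; the zero-fill sensitivity analysis shows by how much. If the relevant database lock has already passed, the change should be recorded in the study report, as the SAP introduction requires for departures from the planned analyses.
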